15 STATISTICAL CONSIDERATIONS

15.1 VBD Subtype Designation

Women with VBD-c will be distinguished from those with VBD-p based on the presence of a COPC. The Institute of Medicine's 2011 report, *Relieving Pain in America*, identified 9 COPCs that predominantly affect women and frequently co-occur with VBD.⁹³ The presence of a COPC will be determined using the COPC survey. This is an easy-to-complete form including modules with check-box questions and a body mannequin to determine the presence of 9 COPCs: 1) FMS, 2) TMD, 3) back pain, 4) IBS, 5) chronic tension-type headache, 6) chronic migraine, and 7) chronic fatigue syndrome, 8) endometriosis, and 9) interstitial cystitis. Women with VBD and no COPCs will be designated as VBD-p, while women with VBD and ≥ 1 COPC will be designated as VBD-c. These criteria will be used as a primary method to distinguish between VBD-p and VBD-c in this study.

We, however, acknowledge that the criteria to distinguish VBD subtypes needs further exploration. In particular, it is possible that the optimal cutoff for VBD-c requires more than one COPC to be present. Therefore, as a secondary method to characterize VBD subtypes, we will calculate a continuous COPC 'centralness' score defined as the number of COPCs present ranging from 0 to 9. This continuous COPC score will be used to identify the optimal cutoff value between VBD-p and VBD-c in terms of treatment response.

To further characterize the two VBD subtypes, we will also measure generalized pain at 'neutral' non-pelvic sites using a quantitative sensory testing approach designed by [name] and colleagues.^{94, 95} The 3 neutral sites (deltoid muscle, shin, trapezius) are remote from the pelvic region and not used for diagnosing other pain conditions, but reflect an individual's overall

pressure pain sensitivity.⁹⁸⁻¹⁰⁰ An algometer will be applied to the 3 sites, with continuously ascending pressure at a rate of 1 kg/s to a maximum of 10 kg. Participants will indicate when the evoked sensation first becomes painful. A composite pressure pain threshold (PPT) score will be compared between VBD-c and VBD-p subgroups using ANCOVA. We would expect women with VBD-p to have higher PPT scores (less pain) and women with VBD-c to have lower scores (more pain) at these sites.

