To answer questions 1a and 1b, we will fit mixed model repeated measures (MMRM) models which account for missing data as an integral part of the analyses under the assumption of ignorable missing. To answer question 1a, the MMRM model includes longitudinal pain score (0-10 NRS on Tampon Test) as a continuous outcome variable; includes fixed effect terms for treatment (nortriptyline, lidocaine/estradiol, and their interaction), visit, treatment visit interaction, center, and fixed effect covariates vector including age, VBD subtype (binary variable where VBD-c is coded as 0 and VBD-p coded as 1), race (three levels "white", "black" and "other" race, coded into two binary dummy variables with European American serving as a reference level).

Overall treatment effect of nortriptyline, lidocaine/estradiol, and their interaction will be evaluated using an F-test. If significant ($p < 0.05$), treatment differences (each of 3 treatment groups minus placebo) in the Least-Squares means (LS means), their 2-sided 95% CIs, and associated p-

values will be estimated from the MMRM model. P-values will be compared with the significance threshold Bonferroni-corrected for 3 tests (i.e. alpha 0.0166).

To answer question 1b, we will fit a MMRM model analogous to 1a, with additional terms of VBD subtype visit interaction, treatment VBD subtype interaction, and treatment visit VBD subtype interaction. The significance of the additional interaction terms will be evaluated using a F-test comparing the full model in 1b and the reduced model in 1a. Significant ($p < 0.05$) F-test will suggest that the effect of either nortriptyline or lidocaine/estradiol cream, or both, differ by VBD subtype. In this case, we will compare the LS means of the treatment differences in each treatment-VBD-subtype subgroup, after appropriate Bonferroni correction.

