If the results for question 1a or 1b are statistically significant, the following primary outcomes will be analyzed using the same modeling strategies (models in 1a and 1b above): % decrease in pain score (tampon test) from baseline to the 16-week time point and % decrease in perceived pain on the SF-MPQ from baseline to the 16-week time point. Secondary outcomes include change in mucosal, vulvovaginal muscle, and remote bodily PPTs from baseline to the 16-week time point. Secondary outcomes also include change in pain scores and PPTs from baseline to the 8-week time point and change in pain scores and PPTs from the 16-week to the 24-week time point.

If the result for question 1b is non-significant, we will use the continuous COPC score in model 1b instead of a dichotomous VBD classification to compare treatment success for VBD-p and VBD-c. In addition, we use a binary treatment outcome (achievement of 30% pain reduction) to identify the optimal cutoff of the continuous COPC score in each treatment group.

Secondary analyses of muscle pain based on PPTs will also determine: a) the proportion of women with VBD that have a pelvic muscle pain component; b) differences in the distribution of muscle pain in VBD-p and VBD-c groups; and c) presence of muscle pain to predict treatment outcome. The latter will be tested by including the muscle pain variable (continuous or dichotomous) as part of the fixed effect term in model 1a.

Expected Outcomes. **1)** For women with VBD-p, peripheral lidocaine/estradiol treatment will be more effective than placebo or nortriptyline in reducing numeric pain ratings on the tampon test, perceived pain on the SF-MPQ, and pelvic PPTs on the algometer test at week 8 and week 16. **2)** For women with VBD-c, centrally-targeted nortriptyline treatment will be more effective than placebo or lidocaine/estradiol in reducing numeric pain ratings on the tampon test, perceived pain on the SF-MPQ, and pelvic/remote bodily PPTs on the algometer test at week 16. **3)** For women with VBD-c, combined peripheral and centrally-targeted treatments will be most effective in reducing pain on primary and secondary outcome measures at week 16. **4)** The two VBD subtypes will exhibit differential responses to treatment withdrawal at week 16, such that at the week 24 visit women with VBD-c will exhibit increases in pain after treatment withdrawal compared to women with VBD-p.

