15.6 Sample Size and Power

We are planning to enroll 400 women with VBD, with an estimated attrition rate of 20%. Of note, Reed et al. found that vulvar pain measured on a 0-10 numeric scale has standard deviation 2.0.¹⁰⁴ Salaffi et al¹⁰⁵ noted that 2 points on a 0-10 NRS correspond to a clinically meaningful difference in pain severity. Using these results and assuming the within-subject correlation of 0.5, at a significance level of 0.05, the proposed sample size will provide sufficient power of at least 0.80 to detect differences as small as 0.82 on a 0-10 scale for the overall treatment main effects (3 arms) vs. placebo. To test each individual treatment effect vs. placebo, at a significance level of 0.0167 (Bonferroni-corrected for 3 arms), the proposed sample size can detect differences as small as 0.98 on a 0-10 scale. At a significance level of 0.05, the proposed sample size can detect differences as small as 1.35 and 1.20 on a 0-10 scale for the interaction effect of treatment and each VBD-subtype, given possible splits of 40/60, 50/50, or 60/40 (of note, VBD-p vs VBD-c frequencies were 40/60 at UNC and 50/50 at UCLA clinics in previous studies).

To calculate power for research question IIIa, we used data from our previous study of biomarkers in VBD patients.⁷ Conservatively assuming that VBD-c patients represent 60% (192/320) of the sample and VBD-p patients represent 40% (128/320) of the sample, and adjusting the significance threshold for 4 tier 1 cytokine tests, we will be able to detect mean differences of at least 0.4 SD with the power of 0.84 or greater using a t-test. For IL-8, 0.4 SD translates to approximately 2 pg/mL, and for IL-1ra 0.4 SD translates to 240 pg/mL of the minimal detectable difference. Of note, the mean differences between controls and VBD patients for IL-8 and IL-1ra in our previous study were 4 pg/mL and 300 pg/mL, respectively. Thus, we have sufficient power to detect plausible differences in cytokine levels between the VBD subgroups.

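### A null result on primary question 1b triggers a retest with the continuous COPC score, with no alpha control and nothing barring a subtype claim from it

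*Combined protocol and SAP*

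**What the plan says.** Section 15.1 defines the subtypes by COPC count: "Women with VBD and no COPCs will be designated as VBD-p", and women with one or more are VBD-c. Of this rule it says "These criteria will be used as a primary method to distinguish between VBD-p and VBD-c in this study". It adds that "as a secondary method to characterize VBD subtypes, we will calculate a continuous COPC" score, defined as "the number of COPCs present ranging from 0 to 9", which will serve to look for the best cutoff between the subtypes. Section 15.1 does not make use of the score depend on any test result.

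Section 15.2 answers 1b by extending model 1a "with additional terms of VBD subtype visit interaction, treatment VBD subtype interaction, and treatment visit VBD subtype interaction". The added terms are tested jointly: "Significant ($p < 0.05$) F-test will suggest that the effect of either nortriptyline or lidocaine/estradiol cream, or both, differ by VBD subtype". Bonferroni-corrected comparisons of LS means follow only if that F-test is significant.

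Two paragraphs later Section 15.2 adds the conditional step: "If the result for question 1b is non-significant, we will use the continuous COPC score in model 1b instead of a dichotomous VBD classification". The stated purpose is to compare treatment success between VBD-p and VBD-c. The same paragraph adds a search for the optimal COPC cutoff in each treatment group, based on a 30% pain reduction. No significance level, alpha split or limit on interpretation is attached to either step. Section 15.2 also makes analysis of further primary outcomes conditional on a significant 1a or 1b, without saying whether a significant refit would count as 1b.

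**The concern.** The refit keeps the model, the outcome and the question. Only the coding of the moderator changes, and it is done only after the primary coding has failed. Without a limit on what may be concluded, the hypothesis of differential response by subtype gets a second test exactly when the first was negative, and a correct null could be replaced by a false positive.

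Section 15.1 does rank the score as secondary, but that ranking concerns how subtypes are characterised. It does not say what a significant refit would mean. Elsewhere the plan is explicit: Section 15.4 keeps its secondary biomarker analyses at 0.05 because they are exploratory, and Sections 15.2 to 15.4 apply Bonferroni thresholds to other sets of tests. Neither device is applied to this retest. The two sections also differ on when the score is used: 15.1 sets no condition, while 15.2 uses it in model 1b only after a null.

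**Working it through.** **Inputs from the documents.** The 1b F-test is at 0.05 (15.2). VBD-p is a COPC count of 0, VBD-c a count of 1 or more, and the score runs from 0 to 9 (15.1). On the split, "VBD-p vs VBD-c frequencies were 40/60 at UNC and 50/50 at UCLA clinics in previous studies" (15.6), and 15.6 also considers 60/40. There are 400 women with 20% attrition, so 400 × 0.80 = 320 analysed; the SD is 2.0 and the within-subject correlation 0.5 (15.6). Allocation is 1:1:1:1 (5.3).

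**Assumptions.** The refit is read at 0.05. The distribution of COPC counts among VBD-c women is not in the documents, so several shapes were tried. The number of visits in the model, V, is not stated.

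**Terms tested.** With three treatment terms, the joint test has 3 (treatment × subtype) + (V − 1) (subtype × visit) + 3(V − 1) (treatment × visit × subtype) = 3 + 4(V − 1) df. That is 3 for V = 1, 11 for V = 3 and 15 for V = 4.

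**Plan's own figure.** The binary test alone has level 0.05 by construction. In simulation each test alone rejected in 4.3% to 5.6% of runs (Monte Carlo SE about 0.3 points).

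**Bounds.** P(either) = 0.05 + 0.05 − P(both). If the two tests were identical this is 0.05. If they were independent it is 1 − 0.95² = 0.0975. The binary subtype is a cut of the count, so the truth lies between.

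**Asymptotic result.** Let Q_B = ΣX_j² and Q_C = ΣY_j² over k components, with corr(X_j, Y_j) = r and c the 95th percentile of chi-square on k df. P(Q_B > c or Q_C > c) is then:

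| r | k = 3 | k = 11 | k = 15 |
|---|---|---|---|
| 0.6 | 8.9% | 9.0% | 9.1% |
| 0.7 | 8.5% | 8.6% | 8.7% |
| 0.8 | 7.9% | 8.1% | 8.3% |
| 0.9 | 7.2% | 7.3% | 7.3% |

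**Simulation.** With N = 320, four equal arms, compound symmetry 0.5, SD 2, six assumed count shapes, VBD-p shares of 40%, 50% and 60%, and 6,000 runs per scenario, the absolute correlation between subtype and count was 0.67 to 0.88. The joint error was 6.9% to 8.9%, mostly 7.5% to 8.3%. One four-visit scenario was run and gave 7.1%. If the VBD-c count is taken as 1 + Poisson with mean 0.5 to 2.5, capped at 9, the range narrows to 7.5% to 8.2%.

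**Dependence on the subtype-by-visit term.** The joint F-test includes this term, which is not a treatment interaction. Suppose there is no treatment-by-subtype effect, a 50/50 split (160 per subtype), and an extra subtype difference d at one visit. The noncentrality is d²(1 − 1/V) / [σ²(1 − ρ)(1/160 + 1/160)]. For V = 3 and d = 0.25 it is 0.0625 × 0.667 / (2 × 0.0125) = 1.67, and the binary test alone rejects about 10% of the time. For d = 0.5 it is 6.67, and rejection is about 34%. For V = 4 the rates are almost the same. So both the 5% and the 7% to 9% require this term to be zero as well.

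**Cost of splitting alpha.** At 0.025 per test the joint error is about 4.2% to 4.6% (11 df, r from 0.8 to 0.6). On a 1-df approximation at 80% power, detectable differences grow by (2.241 + 0.842) / (1.960 + 0.842) = 1.10, so the interaction figures in 15.6 go from 1.20 to 1.32 and from 1.35 to 1.49.

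**The case against.** The best defence is that the plan already has a hierarchy. Section 15.1 makes the binary rule primary and the score secondary, and introduces the score because the subtype criteria need more exploration. In 15.2 the refit sits beside a cutoff search, which reads as exploratory. The corrected LS-means comparisons are opened by the significant binary F-test, and nothing says the refit opens them. No threshold is attached to the refit, so a second test at 0.05 is inferred from silence. Nor does the plan promise 5% across both codings; it gives 0.05 for one F-test.

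Much of this stands. A reader might infer that the plan commits the trial to an error rate of about 8% for its subtype claim. The documents do not support that: the level of the refit is unstated, the count distribution is not given, and the F-test mixes treatment and non-treatment interactions. If the sponsor declares the refit exploratory, it adds nothing to the error of the 1b test.

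What does not stand is that no change is needed. The conditional trigger is an operative rule in the text, and the secondary label in 15.1 neither removes it nor says what a positive refit may support.

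**Conclusion.** The point holds in a conditional form. Section 15.2 retests a primary question only when the first test is null, with no alpha control and no limit on the claim. If the refit is read at 0.05, the chance of at least one false positive F-test is roughly 7% to 9%. This rests on assumed COPC-count distributions and on a null for all tested terms, including subtype-by-visit. The cutoff search is not counted.

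Two stronger readings should be avoided. One is a flat inflation to 8%, for the reasons above. The other is that the error is always at least 1.5 times 5%, that is 7.5%: the lower scenarios (6.9%, 7.1%) fall short of it. Confidence is high that the trigger exists and is uncontrolled, and moderate on its size.

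**What to change.** In Section 15.2:

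- Delete the condition that 1b be non-significant, and run the continuous-score model whatever the 1b result. This also brings 15.2 into line with 15.1.
- State that this model and the cutoff search are supportive and cannot establish a subtype difference when the binary 1b test is null.
- State that a significant continuous-score result does not count as a significant 1b for opening the further outcomes.

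This needs no added data, participants or power. The cost is that a null 1b can no longer be turned into a positive claim.

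Giving the continuous score confirmatory status, for example under Holm with the smaller p-value tested at 0.025, is not a wording change. The interaction detectable differences in 15.6 would have to be restated about 10% larger, and the primary coding would give up power to a secondary one. The supportive label is the better choice unless the sponsor accepts that cost.

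### The COPC cutoff is sought within each arm on a 30% responder outcome, so it cannot separate prognosis from treatment benefit, and it need not give the single boundary section 15.1 asks for

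*Combined protocol and SAP*

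**What the plan says.** Section 15.1 keeps a simple primary rule: "Women with VBD and no COPCs will be designated as VBD-p", and one or more COPCs makes VBD-c. It then adds, "as a secondary method to characterize VBD subtypes", a count "defined as the number of COPCs present ranging from 0 to 9", and gives it a purpose: "This continuous COPC score will be used to identify the optimal cutoff value between VBD-p and VBD-c in terms of treatment response". That describes one boundary, defined by response to treatment.

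Section 15.2 puts this into practice in a paragraph that opens "If the result for question 1b is non-significant". Two things follow. Model 1b is refitted with the continuous COPC score in place of the binary subtype. The second step is the cutoff search itself: "we use a binary treatment outcome (achievement of 30% pain reduction) to identify the optimal cutoff of the continuous COPC score in each treatment group".

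For this search the plan does not give:
- a criterion for the optimum
- a comparison with placebo
- a rule for reducing four results to one
- a correction for choosing and reporting the cutoff on the same data
- the pain measure and visit that define the 30%, or how women without that visit are counted

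**The concern.** The trial asks which women respond to peripheral and which to central or combined treatment. A cutoff answers that only if the difference between treatments changes across it. A search inside one arm has no comparison group. If women with more COPCs improve less whatever they receive, every arm, placebo included, will tend to show a cutoff although no treatment works better on one side of it. The reverse can also happen: a real difference in benefit can be invisible inside the active arm.

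At stake is a prognostic threshold being reported as the boundary between treatment-relevant subtypes. This would happen after the planned subtype test had come out non-significant, when a positive-looking secondary result draws most attention.

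**Working it through.** The plan states no error rate or power for the cutoff search, so there is no figure to reproduce.

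**Inputs from the documents.** Section 15.6: 400 women and 20% attrition, so 400 × 0.8 / 4 = 80 retained per arm; VBD-p/VBD-c splits of 40/60 and 50/50, so 32 to 40 women per arm with no COPC. Section 5.3: four arms, 1:1:1:1. Section 15.1: a count of 0 to 9, so up to nine possible cutoffs.

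**Inputs assumed.** Responder rates, the COPC distribution above zero, the Youden index as criterion, and a test at the chosen cutoff. The documents give none of these.

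**Step 1: arithmetic, no simulation.** Take assumed responder rates for low and high COPC.

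| | Low COPC | High COPC | Gap within arm |
|---|---|---|---|
| Placebo | 45% | 20% | 25 points |
| Cream | 60% | 35% | 25 points |
| Benefit of cream | 15 points | 15 points | difference 0 |

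COPC does not change the benefit, yet each arm shows a 25-point gap for the search to find. Now let cream give 45% in both strata with placebo unchanged. The benefit is 45 - 45 = 0 points in low COPC and 45 - 20 = 25 points in high COPC, but the gap within the cream arm is 0.

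**Step 2: how often, with a smooth prognostic effect.** Simulated trials of 4 × 80 women; COPC zero with probability 0.4 or 0.5, otherwise declining as 0.6^k; logit of response = 0.2 + slope × COPC, identical in all arms; cutoff 1 to 6 maximising the absolute Youden index; chi-square test at that cutoff. The condition on 1b is not applied.

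| Slope | Arms with p<0.05 | Trials with at least one such arm |
|---|---|---|
| 0 (no association) | 14-15% | 46-48% |
| -0.1 | 23-25% | 65-67% |
| -0.3 | 60-65% | 98% |

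All four arms choose the same cutoff in about 2-4% of these trials. Four different cutoffs occur in about 6-14%.

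**Step 3: a different model.** 3,000 trials, a true step at two or more COPCs, cutoffs 1 to 9.
- Prognostic only (rates as in the first table, plus nortriptyline 60%/35% and combination 70%/45%): nominally significant in 57-66% of trials per arm and in at least one arm in 97-98%. The arms disagree in 74-83% of trials, so they agree in about 17-26%. Four different cutoffs occur in 0.6-0.8%.
- No association: 13-16% per arm, at least one arm in 45-47%, disagreement in 97%, four different cutoffs in 10-11%.
- Benefit of cream only in high COPC, cream arm flat: the cream-arm search is significant in 14%, which is its no-association rate.
- COPC purely predictive, placebo flat: the cream and nortriptyline arms find the true cutoff in 65-72%. The search can therefore work when COPC has no prognostic role, but the plan does not check that condition.

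**Step 4: a between-arm contrast.** In the step model, the cutoff is chosen on the cream-minus-placebo difference in the COPC effect. Its largest |z| exceeds 1.96 in 19-20% of trials when COPC is purely prognostic, against 18-19% with no association. The contrast does not mistake prognosis for benefit. Its excess over 5% comes from searching over cutoffs, so it needs correction.

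**The case against.** Much of the case for the plan stands.

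- The analysis is secondary. It changes neither the 1a nor the 1b test, and section 15.1 itself says the subtype criteria need more work.
- The refit of model 1b with continuous COPC carries treatment-by-COPC terms across arms. It is a sound analysis of effect modification, but it does not produce a cutoff; only the within-arm search does.
- The search runs only if 1b is non-significant, and 1b jointly tests a subtype-by-visit term. A purely prognostic COPC effect on change can make 1b significant, and the search is then not run. One simulation (320 women, SD 2, correlation 0.5, responder slope about -0.27) had 1b reject in 58-66% of trials with baseline as an outcome visit, and in 15-21% with post-baseline visits only. The documents do not settle which applies. The percentages in the working are therefore not error rates for the plan as a whole.

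A reader might infer more than the documents support:

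- *That the search simply finds women who improve anyway.* This is literally true only of the placebo arm. In an active arm it finds who improves on that treatment, for mixed reasons.
- *That VBD-c ends up with four definitions.* Four different cutoffs is the extreme case, and section 15.1 keeps one or more COPCs as the primary rule.
- *That treatment choice will be misdirected.* The documents do not say that the cutoff will guide treatment.
- *That the 30% line conflicts with section 15.6, which cites that "2 points on a 0-10 NRS correspond to a clinically meaningful difference in pain severity".* On a whole-number scale a 30% fall needs 1 point from 3 (1/3 = 33%), 2 points from 4 to 6, and 3 points from 7 to 10. Among the tampon scores that section 5.2 admits, the line falls below 2 points only at exactly 3.

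**Conclusion.** The concern holds as a limited one about a secondary analysis. As written, the within-arm responder search cannot separate prognosis from treatment benefit, and it can return different cutoffs by arm where section 15.1 wants one boundary "identify the optimal cutoff value between VBD-p and VBD-c in terms of treatment response". This follows from the missing between-arm contrast and needs no simulation.

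The size does rest on assumptions. The share of arms with a nominally significant cutoff under pure prognosis runs from about 23% to 65% as the assumed slope goes from -0.1 to -0.3. Agreement of all four arms is the exception in both models: about 2-4% with a smooth slope, and 17-26% with a sharp prognostic step. The nominal test at the chosen cutoff is itself an assumption, since the plan declares none. The primary conclusions of Aim 1 are not affected.

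**What to change.** Replace the cutoff sentence in section 15.2 with wording such as:

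*A single COPC cutoff c, common to all arms, will be chosen by the joint treatment-by-(COPC ≥ c) contrast in week-16 tampon pain adjusted for baseline, using all four arms together and covering active versus placebo and peripheral versus central treatment. The candidate range of c will be fixed in advance. The chosen cutoff and its contrast will be reported with bootstrap or permutation correction for selection, and labelled hypothesis-generating.*

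Keep the 30% responder rate by arm as a descriptive display only, stating the pain measure, the visit and how women without that visit are counted. Align section 15.1 so that both sections describe one cutoff. Keep the continuous-COPC refit of model 1b as it is.

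A separate cutoff for each active arm against placebo would not be enough: it could still give three boundaries.

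The cost is SAP wording and a resampling step on the same data. The downside is that the cutoff will be less precise and may prove not estimable. If so, that should be reported as the result.

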5.3 Baseline Evaluation Phase and Randomization

Immediately following screening, research participants will complete all baseline assessments, including 1) completion of validated questionnaires to measure perceived pain, health, mood, and sexual function 2) vulvar exam and quantitative sensory testing to measure pressure pain thresholds at local (vaginal) and remote body sites, and 3) collection of biologic samples to measure local (vaginal) and systemic (blood) cytokines and miRNAs. The complete schedule of assessments to be obtained during the baseline visit is outlined in **Appendix A**.

Participants who fulfill all the inclusion criteria and none of the exclusion criteria will be randomly assigned on a 1:1:1:1 ratio to one of four treatment groups:

- 5% lidocaine/0.5mg/ml 0.07% estradiol compound vaginal cream + placebo pill
- placebo vaginal cream + nortriptyline pill
- 5% lidocaine/0.5mg/ml 0.07% estradiol compound vaginal cream + nortriptyline pill
- placebo vaginal cream + placebo pill

Medication assignments will be determined by the Duke Clinical Research Institute (DCRI) using randomized blocks, and then stratified by enrollment site. The DCRI will create a SAS program to generate the random sequence that will be loaded in RedCap. Participants and research personnel will be blinded to medication assignment.

[figure not shown]
During the baseline visit, participants will be counseled on optimal study medication administration. Participants will receive a written description of the study with contact numbers of study staff to present to their usual care provider(s).

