To answer question 3b, we will fit a MMRM model analogous to 1a, with additional terms of treatment cytokine (in blood and vaginal samples) interaction, visit cytokine interaction, and treatment visit cytokine interaction. Significance of additional interaction terms will be evaluated using an F-test. Significant ($p < 0.05$) F-test will suggest that treatment effects by nortriptyline or lidocaine/estradiol cream or both, are modified by cytokines.

Secondary analyses for Aim 3 will include the association of Tier 2 biomarkers (cytokines and miRNAs) with VBD subtype and interaction with treatment response. These analyses will be analogous to those specified for questions 3a and 3b, with p-value thresholds kept at 0.05 due to exploratory nature of these analyses. In our secondary analyses we will also evaluate the change of biomarker concentrations (blood and vaginal samples) over time (at 0, 8, 16, and 24 weeks) in each treatment group and VBD subtype. We hypothesize that these biomarkers may serve as intermediate phenotypes for treatment success in VBD patient subgroups.

Expected Outcomes. 1) Women with VBD-p will have higher levels of inflammatory mediators in peripheral vaginal samples, while women with VBD-c will have higher levels of inflammatory mediators in circulating blood measured at the baseline visit (0 weeks). 2) Abnormalities in baseline vaginal cytokine and miRNA biomarkers will predict a positive response to peripheral lidocaine/estradiol treatment, while abnormalities in blood biomarkers will predict a positive response to centrally-targeted nortriptyline or combined treatment. 3) Peripheral treatment will resolve abnormalities in vaginal biomarkers evaluated at 8, 16, and 24 weeks, while central treatment will resolve abnormalities in blood biomarkers evaluated at 16 weeks.

All analyses will be performed using the Intent-to-Treat (ITT) population. The ITT population will include all randomized participants. Participants will be grouped according to their randomized allocation, regardless of whether the allocated therapy was administered or switched.

Any deviations from the statistical analyses described above, due to unforeseen circumstances, will be documented in the Statistical Analysis Plan (SAP).

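### The muscle-pain term added to model 1a cannot separate a higher pain level from a different response, so it does not test whether muscle pain predicts treatment outcome

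*Combined protocol and SAP*

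**What the plan says.** Section 15.2 lists three secondary analyses of muscle pain. The third is "presence of muscle pain to predict treatment outcome", and the method is "including the muscle pain variable (continuous or dichotomous) as part of the fixed effect term in model 1a". For model 1a, the same section says that "the MMRM model includes longitudinal pain score (0-10 NRS on Tampon Test) as a continuous outcome variable" and that it "includes fixed effect terms for treatment (nortriptyline, lidocaine/estradiol, and their interaction), visit, treatment visit interaction, center, and fixed effect covariates vector including age", followed by VBD subtype and race. The only interactions are nortriptyline by cream and treatment by visit. Baseline pain is not among the listed covariates.

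For two parallel questions the plan goes further. Model 1b, on VBD subtype, is model 1a "with additional terms of VBD subtype visit interaction, treatment VBD subtype interaction, and treatment visit VBD subtype interaction". Question 3b in Section 15.4, on biomarkers as predictors of response, is model 1a "with additional terms of treatment cytokine (in blood and vaginal samples) interaction, visit cytokine interaction, and treatment visit cytokine interaction". In both, the added interaction terms are tested by an F-test. No such terms are named for muscle pain.

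**The concern.** A variable predicts treatment outcome in one of two senses. It can modify the benefit of a treatment, which needs an interaction with treatment. Or it can be prognostic for improvement, which needs an interaction with visit, a change outcome, or adjustment for baseline pain. Model 1a with one added muscle-pain term has none of these.

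Women with tender pelvic muscles may simply report more pain on tampon insertion at every visit, including before treatment. Analysed as written, that constant difference could be reported as muscle pain predicting treatment outcome. The pattern the trial was designed around, where one group benefits from the peripheral drug and the other from the central drug, could leave no trace in the coefficient.

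**Working it through.** The plan gives no power, alpha or effect size for this analysis, so there is no stated figure to reproduce.

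**Inputs.** From Section 15.6: SD 2.0, within-subject correlation 0.5, 400 women with 20% attrition, so 400 × 0.8 = 320. From Section 5.3: allocation 1:1:1:1, so 80 per arm. Assumed: two-sided 5% level, equal correlation between visits, three post-baseline visits in the outcome, half the women with muscle pain.

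**1. Constant difference, no influence on response.**
- SD of a woman's mean over three visits: 2.0 × √((1 + 2 × 0.5)/3) = 1.633.
- SE of the muscle-pain coefficient: 1.633/√(320 × 0.5 × 0.5) = 0.183.
- Difference 0.4: z = 0.4/0.183 = 2.19; rejection Φ(2.19 − 1.96) = 59%.
- Difference 0.6: z = 0.6/0.183 = 3.29; rejection Φ(3.29 − 1.96) = 91%.

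A simulation with these inputs (4,000 trials per setting) gave 59% and 91%. The joint test of the treatment-by-muscle-pain terms rejected in 5.2% and 4.7%.

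**2. Sensitivity to prevalence.** The SE is 1.633/√(320 × p × (1 − p)).

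| Share with muscle pain | SE | 0.4 points | 0.6 points |
|---|---|---|---|
| 20% | 0.228 | 42% | 75% |
| 30% | 0.199 | 52% | 85% |
| 50% | 0.183 | 59% | 91% |

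**3. Week 0 kept in the outcome.** The plan does not say whether it is. With four visits the SE is 2.0 × √((1 + 3 × 0.5)/4) × √(2/160) = 0.177. A simulation of 2,000 trials per setting gave:

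| True situation | Planned main effect | Treatment-by-muscle-pain test |
|---|---|---|
| No effect of muscle pain | 4.8% | 5.7% |
| Constant +0.5 points, no influence on response | 82% | 5.1% |
| Cream works only without muscle pain, nortriptyline only with it (1.35 points, weeks 8 and 16) | 4.5% | 99.8% |
| Active arms work only without muscle pain (1.35 points, weeks 8 and 16) | 82% | 78% |
| Course 1 point worse after baseline in every arm | 99% | 5% |

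**4. Why the second and fourth rows look alike.** The coefficient averages the with-minus-without difference over arms and visits. In the fourth row the difference is 1.35 in three of four arms at two of four visits: 1.35 × 3/4 × 2/4 = 0.51, nearly the same as a constant 0.5. In the third row the arm differences are 0 (placebo), +1.35 (cream), −1.35 (nortriptyline) and 0 (combined, where the simulation gives 1.35 points of benefit to both groups). Their average is zero, so the planned test has nothing to detect.

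**The case against.** Four points can be made for the plan.

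- **The aim may be prognosis.** Section 15.2 describes the primary endpoints as net change, and applies the same models to percentage decrease in pain if question 1a or 1b is significant. With that outcome, a muscle-pain main effect could be read as prognosis for improvement. This stands, so a reader who infers that no prognostic reading is possible goes too far. But the muscle-pain sentence points to model 1a, whose defined outcome is the longitudinal score. Even with percentage decrease, a main effect would not test differential benefit.
- **The coefficient is not blind to response.** A reader might infer that it shows only that women with muscle pain hurt more at every visit. The last two rows of the week-0 table refute this: real response differences also feed into it. The fault is that they cannot be told apart from level.
- **The wording is loose.** The phrase about the fixed effect term might have been meant to include interactions. If so, they should be named, as they are for 1b and 3b.
- **The percentages are not false-positive rates.** A reader might take 59% and 91% as the chance of a wrong published claim. They are the power of a valid test to find a level difference that was put in. The harm lies in calling that difference prediction of treatment outcome.

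**Conclusion.** The concern holds. As written, the muscle-pain analysis cannot separate a constant difference in pain level from a difference in response, and it can miss opposite effects of the two drugs. This follows from the model's structure and does not depend on the assumed numbers.

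The size does depend on them. For level differences of 0.4 to 0.6 points and a prevalence of 20% to 50%, the planned term is significant in 42% to 91% of trials when muscle pain has no influence on response. The interaction test stays near 5% whatever the level difference, because the muscle-pain main effect absorbs it. The prevalence and the size of the shift are assumptions, not figures from the plan.

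A reader might infer that the main Aim 1 conclusions are at risk. The documents do not support that: this is one item in a set of secondary analyses, and no primary test or sample-size statement rests on it.

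**What to change.** In Section 15.2:

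- State that the baseline muscle-pain value is used. Appendix A schedules muscle PPTs at every visit, and Section 15.2 also treats their change as an outcome, yet the text does not say which value enters the model.
- Add muscle pain × visit, treatment × muscle pain and treatment × visit × muscle pain to model 1a, following 1b and 3b.
- Test the treatment-by-muscle-pain terms jointly for prediction of benefit, and report the 16-week contrast.
- Report prognosis separately, either from muscle pain × visit or from a model adjusted for the baseline tampon score. In the adjusted model, week 0 must leave the outcome vector.

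The cost is SAP wording and lower power. At 80% power and a 5% level with a 50% prevalence, the main effect detects 2.80 × 0.183 = 0.51 points. The 16-week contrast for one active arm against placebo has 40 women per cell, an SE of 2.0 × √(4/40) = 0.632, and detects 2.80 × 0.632 = 1.77 points. A non-significant interaction should therefore be reported with its confidence interval and not as absence of modification.
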